8.3. Exclusion Criteria

The participant may not enter the trial if ANY of the following apply:

• Participant is unwilling or unable to give informed consent for participation in the trial.

IRAS ID: 301556

9. TRIAL PROCEDURES

None

9.1. Recruitment

Recruitment centres will be selected from the Wessex Deanery via the Wessex Research Collaborative. Each site will have a trainee associate PI who will be responsible for identifying patients presenting with gallstone disease from the emergency take list. Patients will be approached during their index admission and given information about the study. If they agree to participate, they will be consented and registered by an appropriately trained member of the research team. Patients will only be approached on multiple occasions if they have specifically asked to be given more time to consider their decision or discuss with others.

9.2. Screening and Eligibility Assessment

There is no specific time limit between screening and registration but the patient must be recruited and registered during their index hospital admission.

Screening will involve reviewing the patient's medical notes and imaging results to ensure that there is a clear diagnosis of gallstone-related disease. If the diagnosis is unclear (e.g. pancreatitis without confirmation of gallstones) the patient should either be excluded or rescreened once further investigations have been carried out. A screening log will be maintained at each site, documenting eligibility and if eligible, the reasons for patients not recruited (e.g. not approached, declined).

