6. OBJECTIVES AND OUTCOME MEASURES

Objectives	Outcome Measures	Timepoint(s) of evaluation of this outcome measure (if applicable)
Primary Objective To compare the rate of gallstone- related hospital re-admission between patients treated operatively and non-operatively	Number and percentage of patients readmitted to hospital with gallstone-related disease by each timepoint.	30 days, 1 year, 3 years
1. To compare morbidity in operative and non-operative groups 2. To compare mortality in operative and non-operative groups 3. To compare quality of life in operative and non-operative groups	Number and percentage of patients with complications in each group Number and percentage of patients who have died in each group Gastrointestinal Quality of Life Index (GIQLI) in each group	30 days, 1 year, 3 years
Exploratory Objectives To assess the result of frailty on		

IRAS ID: 301556

morbidity, mortality and quality of	Morbidity, mortality and quality of life	30 days, 1 year, 3	l
life (as defined above)	according to Rockwood frailty score	years	l
To assess whether frailty affects	Comparison of Rockwood frailty score in		
whether or not surgery is carried	operative and non-operative groups both		
out	before and after surgery.		l
	- ,		

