9.6. Baseline Assessments

Demographic data will be collected from the participant's medical records. Frailty will also be assessed at baseline

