9.7. Subsequent Visits

Patients will be contacted by telephone at 30 days, 1 year and 3 years from registration. Prior to any contact, the hospital EPR and CHiE will be checked to ensure that the patient is still alive.

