12.2. Description of Statistical Methods

Continuous data will be summarized using descriptive statistics (mean, median, standard deviation, quartiles, minimum and maximum) and categorical data will be summarized using counts and

IRAS ID: 301556

percentages. The proportion of patients undergoing operative compared to non-operative treatment will be reported.

Primary endpoint

The primary endpoint will be reported as the percentage of patients re-admitted with gallstone related problems after operative vs non-operative management during their index admission.

Secondary endpoints

Data will be reported at 30 days, 1 year and 3 years. Patients who have had complications or have died in each group will be reported as a number and percentage. Comparison between groups will be carried out using Chi squared test. Gastrointestinal Quality of Life Index (GIQLI) in each group will be reported as a median and range. Paired T test will be used to compare groups.

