12.4. Analysis Populations

All patients as registered. Comparisons will be made between groups who had surgery during/after their index admission and those who were treated non-operatively in assessing the primary endpoint.

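### Registration, and with it the single baseline frailty score, may come after an index-admission operation, so some early operative deaths can be missing from the 30-day results and a pre-operative Rockwood score is not secured

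*Protocol*

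**What the plan says.** **Entry.** Protocol section 9.1 has the site trainee "identifying patients presenting with gallstone disease from the emergency take list" and adds: "Patients will be approached during their index admission and given information about the study". Section 9.2 sets the only time limit: "There is no specific time limit between screening and registration but the patient must be recruited and registered during their index hospital admission". Section 9.2 also lets a patient with an unclear diagnosis be rescreened after more tests, and section 9.3 sets no limit on the time a patient may take to decide. Sections 8.3 and 9.3 require the patient's own signed and dated consent.

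**Exposure and analysis.** Section 12.2 describes patients "re-admitted with gallstone related problems after operative vs non-operative management during their index admission". Section 12.4 compares "groups who had surgery during/after their index admission and those who were treated non-operatively" and takes the registered patients as the analysis population. Mortality and morbidity by group at 30 days, 1 year and 3 years are secondary outcomes (section 6). Section 9.7 times follow-up from entry: "Patients will be contacted by telephone at 30 days, 1 year and 3 years from registration".

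**Frailty.** One exploratory objective in section 6 begins "To assess whether frailty affects" and goes on to ask about the choice of surgery. Its outcome measure names Rockwood scores before as well as after the operation. Section 9.6 says only: "Frailty will also be assessed at baseline". Section 13.2 lets the score come from the medical record, with the patient questioned if it is not recorded there. The schedule in Appendix A has no frailty row and no visit tied to an operation.

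**The concern.** In a cohort study that compares treatments, a patient should enter before the exposure is received, or the analysis should at least be able to tell who did not. Here a patient can be operated on, recover on the ward, and only then be approached. Patients who enter this way have by definition survived the operation in a state to consent. Those who did not survive, or lost capacity, leave no record in the analysis set. Early mortality and morbidity are the outcomes on which operative and non-operative care of older patients will be compared, so the loss falls where readers will look.

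Changing the time origin does not cure this, because moving the clock back to admission does not restore people who were never registered. Nor can a later analysis plan recover them; the entry rule belongs to the protocol.

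The frailty question has a related weakness. Whether frailty influences the decision to operate can only be answered with a score describing the patient before that decision. If the score is taken at registration, registration follows surgery, and the score reflects the patient's condition that day, it is partly a result of the operation.

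**Working it through.** **Can exposure precede entry?**
1. Both exposure definitions (sections 12.2 and 12.4) count surgery in the index admission as operative treatment. They differ on surgery after discharge and should be reconciled, but that does not affect this step.
2. Registration may fall anywhere in the index admission (sections 9.1 and 9.2).
3. So an index-admission operation may come first. Surgery after discharge cannot, because registration must already have happened.

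**Who is then missing?**
4. Entry needs personal consent (sections 8.3 and 9.3), and only registered patients are analysed (section 12.4).
5. So anyone who dies or loses capacity before registration is missing, in either group. Patients registered before surgery are counted whatever happens later, as are patients registered after surgery who die afterwards.

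**Size.** The protocol gives no figure to reproduce here; its sample size concerns readmission. It gives neither early operative mortality nor the timing of registration, so the following is illustration only. Let m be true early operative mortality and f the share of those deaths that occur before registration. Then

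observed mortality = m(1 − f) / (1 − m·f), and deaths missed among N operated = N·m·f.

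Take N = 261, which is 90% of the recruitment target of 290 (section 12.3 expects 1:9). Treating all 261 as operated on before registration puts the counts at the high end.

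| assumed m | f = 25% | f = 50% | f = 75% |
|---|---|---|---|
| 1% | 0.75% (0.7 missed) | 0.50% (1.3) | 0.25% (2.0) |
| 3% | 2.27% (2.0) | 1.52% (3.9) | 0.77% (5.9) |
| 5% | 3.80% (3.3) | 2.56% (6.5) | 1.30% (9.8) |

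Example: m = 3%, f = 50% gives 0.015 / 0.985 = 1.52%, and 261 × 0.03 × 0.5 = 3.9 deaths missed. If everyone is registered before surgery, f = 0 and nothing is lost.

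**Direction between groups.** The same formula applies to non-operative patients. Assume true early mortality of 3% operative and 5% non-operative, a difference of 2.00 points.
- Half of early deaths missed in both groups: 2.56% − 1.52% = 1.04 points, so the difference shrinks.
- Half missed in the operative group only: 5.00% − 1.52% = 3.48 points, so it grows.

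Nothing in the protocol says which case is closer to the truth.

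**Frailty, side by side.**
- Section 6 names scores on both sides of the operation, and for both groups, although non-operative patients have no operation to date a score against.
- Section 9.6 gives one baseline score with no stated reference state.
- Section 13.2 permits a score from the notes, which may pre-date surgery, or from questioning, which need not describe that time.
- Appendix A schedules neither score.

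The pre-operative score is named as an outcome measure, but no procedure secures it.

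**The case against.** The strongest reply is that the protocol already leans towards early entry and partly covers the losses. Patients are found from the emergency take list, which favours approach soon after arrival. Consent is dated, hospital records are source data, and the case report form is not at hand, so the relevant dates cannot be called missing. The screening log records eligible patients who were not recruited and why. Section 6 names a pre-operative frailty score, and section 13.2 allows it to come from the record. The primary endpoint is readmission, on which no effect has been shown.

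Most of this stands, and it limits the point. What it does not do is close the gap. Early approach is likely but not required. The log is not required to hold treatment received or vital status, so as written it cannot quantify the loss. A score from the notes is allowed, but no reference state is fixed.

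Four stronger readings are tempting and not supported:
- *Early operative deaths never enter the cohort.* Only deaths or loss of capacity before registration are missed.
- *The comparison is biased in favour of surgery.* Non-operative patients can be lost in the same way, so the direction is open.
- *Operative mortality will be seen at about half its true value.* That needs about half of the early operative deaths to precede registration, and the protocol gives no such figure.
- *The plan is to answer the frailty question with postoperative scores.* Section 6 intends otherwise; the intention is simply not carried into the procedures.

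**Conclusion.** The point holds in limited form. Followed as written, the protocol admits some operative patients only if they survived surgery able to consent. Absolute early operative mortality and morbidity may therefore be understated. The direction of any bias between groups is not known, and its size cannot be derived from the protocol; the range of about 0.7 to 9.8 missed deaths among 261 operated patients rests wholly on assumed mortality (1% to 5%) and an assumed share of deaths before registration (25% to 75%).

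For frailty, the defect is a mismatch between a named pre-operative score and procedures that provide one baseline not tied to the operation.

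The consequences shown concern secondary and exploratory outcomes. The matter is worth correcting because the remedy is cheap and patients never registered cannot be recovered at analysis.

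**What to change.** 1. **Section 9.6.** State that the baseline Rockwood score describes the patient before the acute illness, taken from notes or history whenever registration happens. Reconcile this with the pre- and post-operative scores in section 6 and with Appendix A, including what is meant for non-operative patients.
2. **Section 9.2.** Ask that every patient, whatever treatment follows, be registered as early in the admission as possible and, where feasible, before any index-admission operation. Apply this to all patients: a rule for operated patients alone would create a new difference in entry conditions between the groups.
3. **Section 12.** Use the dates of admission, operation and registration to identify patients registered after surgery, and report 30-day mortality and morbidity with and without them. Show both results, since dropping these patients also removes those operated on quickly.
4. **Screening log.** Within the study's consent terms and approvals, add anonymised counts of eligible patients who died or lost capacity before registration, by treatment received.

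The cost is amendment wording, a little more logging and analysis, and fewer patients in the 30-day sensitivity analysis. Clinical care is unchanged.

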9.3. Informed Consent

The participant must personally sign and date the latest approved version of the Informed Consent form before any trial specific procedures are performed.

Written and verbal versions of the Participant Information and Informed Consent will be presented to the participants detailing the nature of the trial; what it will involve for the participant; the implications and constraints of the protocol; the known side effects and any risks involved in taking part. It will be clearly stated that the participant is free to withdraw from the trial at any time for any reason without prejudice to future care, without affecting their legal rights and with no obligation to give the reason for withdrawal.

The participant will be allowed as much time as wished to consider the information, and the opportunity to question the Investigator, their GP or other independent parties to decide whether they will participate in the trial. Written Informed Consent will then be obtained by means of participant dated signature and dated signature of the person who presented and obtained the Informed Consent. The person who obtained the consent must be suitably qualified and experienced, and have been authorised to do so by the Chief/Principal Investigator. A copy of the signed Informed Consent will be given to the participant. The original signed form will be retained at the trial site.

9.4. Randomisation

IRAS ID: 301556

Not applicable – observational trial

9.5. Blinding and code-breaking

Not applicable – observational trial

9.6. Baseline Assessments

Demographic data will be collected from the participant's medical records. Frailty will also be assessed at baseline

9.7. Subsequent Visits

Patients will be contacted by telephone at 30 days, 1 year and 3 years from registration. Prior to any contact, the hospital EPR and CHiE will be checked to ensure that the patient is still alive.

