7. TRIAL DESIGN

This is an observational multicentre cohort study which will take place in a number of hospitals in Wessex. Patients will be recruited to the trial during admission for gallstone disease and followed up for 3 years after this admission. At each follow up timepoint patients will be contacted and asked to complete a quality of life questionnaire and will also be asked whether they have had any further admissions with gallstone related disease. Follow up information may also be obtained from hospital and GP records where appropriate.

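### Follow-up is timed from registration during the index admission and no outcome is given its own start date, which distorts the 30-day comparisons

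*Protocol*

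**What the plan says.** Four parts of the protocol bear on when the clock starts.

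- Section 9.7: "Patients will be contacted by telephone at 30 days, 1 year and 3 years from registration". Section 9.2 adds that "the patient must be recruited and registered during their index hospital admission", with no time limit between screening and registration.
- Section 7: patients are "followed up for 3 years after this admission". It also says that they are asked about further gallstone admissions at each follow-up timepoint, and that hospital and GP records may be used.
- Section 6 defines the primary outcome as "Number and percentage of patients readmitted to hospital with gallstone-related disease by each timepoint" and lists complications, deaths and GIQLI at the same three times. Section 12.2 says of the secondary endpoints: "Data will be reported at 30 days, 1 year and 3 years". Neither section names a start date.
- Appendix A schedules CRF completion and the telephone call at the same three follow-ups.

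The groups are defined in two ways. Section 12.4 compares "groups who had surgery during/after their index admission and those who were treated non-operatively", for the primary endpoint. Section 12.2 reports the primary endpoint "after operative vs non-operative management during their index admission". The lay summary expects some patients to return later for planned surgery and gives no interval. Section 12.1 says that no separate SAP is in use, so the protocol itself has to settle these points.

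**The concern.** Registration is the only working start date in the protocol, and it suits neither of the two things that a 30-day figure is usually read for.

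A readmission can occur only after discharge. A window opened at registration runs while the patient is still an inpatient, so a patient with a longer stay has fewer days in which a readmission can be counted. If operated and non-operated patients differ in length of stay, the primary outcome at 30 days compares unequal time at risk.

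For complications and deaths, the question is what 30 days from registration means for someone operated on later. If that patient counts as operative, the operative group's 30-day result contains time before any operation. The lay summary says that the study is meant to inform discussion of the likely outcomes of each treatment. Early surgical harm is a large part of that discussion, and the 30-day figure could be misread as describing it.

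**Working it through.** The plan gives no figure on this point. The sample size of 260 (290 with losses) is not affected, because its readmission rates of 30% and 5% are tied to no timepoint.

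**1. Readmission window spent in hospital.** Let L be the days in hospital after registration. The protocol gives no value, so L is assumed over a range. The share of a window of W days with no possible readmission is L / W, and the days at risk within 30 days are 30 − L.

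| L (assumed) | Days at risk of 30 | Share of 30 days lost | Share of 1 year (365) lost | Share of 3 years (1,095) lost |
|---|---|---|---|---|
| 3 | 27 | 3/30 = 10% | 0.8% | 0.3% |
| 5 | 25 | 5/30 = 17% | 1.4% | 0.5% |
| 7 | 23 | 7/30 = 23% | 1.9% | 0.6% |
| 10 | 20 | 10/30 = 33% | 2.7% | 0.9% |
| 14 | 16 | 14/30 = 47% | 3.8% | 1.3% |

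If one group stayed 10 days after registration and the other 3, they would have 20 and 27 days at risk, a difference of (27 − 20)/27 = 26%. This describes exposure time only. It would translate directly into readmissions only under a constant hazard, and the protocol does not say which group stays longer.

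**2. Post-operative days seen by the 30-day window.** Let d be the day of surgery counted from registration. The share of the first 30 post-operative days inside the window is max(0, 30 − d)/30.

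| d (assumed) | Share covered |
|---|---|
| 5 | 25/30 = 83% |
| 10 | 20/30 = 67% |
| 15 | 15/30 = 50% |
| 20 | 10/30 = 33% |
| 30 or later | 0% |

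A patient operated on after day 30 was necessarily alive at day 30. That patient therefore adds no death to the operative group's 30-day mortality, by construction. Any 30-day complication or GIQLI score from that patient is pre-operative.

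**3. Dependence on the grouping.** Under section 12.4 a patient operated on after the index admission is operative, so step 2 applies if that grouping is carried over to the secondary outcomes. Under section 12.2 a patient not operated on during the index admission is non-operative, so step 2 falls away for surgery after discharge. Both sentences concern the primary endpoint, and the secondary outcomes have no group definition of their own.

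**The case against.** The strongest reply is that section 9.7 times telephone calls, not outcome windows. A reader might infer from it that every outcome is fixed to registration. The text does not go that far: section 7 gives a different start and the outcome sections give none. This stands, and the defect is an unstated and inconsistent start date. It still needs correcting, because readmissions are asked about and CRFs completed at those same contacts, and no section offers a clock from discharge or operation.

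Second, a reader might infer that the plan promises a 30-day post-operative complication rate and mismeasures it. It does not: section 6 sets complications and deaths per group. A common start at enrolment is a normal choice for comparing management groups, and events while waiting belong to a policy of delayed surgery. This also stands, and it is why the between-group comparison should keep one common origin.

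Third, the pre-operative problem rests on one side of the conflict between 12.2 and 12.4, and on extending 12.4 beyond the primary endpoint. That is correct, so the point is conditional.

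Fourth, lengths of stay and times to surgery are assumed. They are, and only the ranges above can be claimed.

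**Conclusion.** The point holds for the 30-day results and hardly at all for the longer ones. Followed as written, 10% to 47% of the 30-day readmission window is spent in hospital for an assumed stay of 3 to 14 days after registration. At 1 year the share is at most 3.8%, and at 3 years 1.3%. Bias between groups arises only if stay differs between them, and its direction cannot be told from the protocol.

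If the section 12.4 grouping is used for the secondary outcomes, 30-day complications, deaths and GIQLI are wholly pre-operative for patients operated on after day 30, and the post-operative window is cut short for those operated on earlier. How many patients this affects is not known.

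It would go too far to conclude that surgical harm is missed altogether. The 1-year and 3-year windows can capture the complications of delayed surgery.

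**What to change.** 1. In sections 6, 7, 9.7 and 12.2, count 30-day readmission from the index discharge date, among patients discharged alive, using recorded dates.
2. For the between-group comparison of complications and deaths, state one common origin (index admission or registration) and keep it at all timepoints. Starting operated patients at surgery and the others at discharge would give the groups different clocks and favour those who survived to their operation. Starting everyone at discharge would drop deaths and complications of the index admission.
3. Add a separate descriptive rate of complications and deaths within 30 days of the operation date, for all operated patients. Label it as not being the between-group comparison.
4. Reconcile sections 12.2 and 12.4 on who counts as operative, and say which definition applies to the secondary outcomes.

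The cost is wording plus the discharge and operation dates on the CRF, taken from records that section 7 already allows. Call dates need not move. Because a window from discharge closes after the 30-day call, the readmission item should be completed from records once the window has ended.
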